12.2.4.2. Secondary analyses

When a comparison between an AZD3293 dose group and the placebo group is statistically significant on the primary efficacy endpoint, the secondary efficacy endpoints for the AZD3293 dose group will be tested through a graphical approach. The specific graph is detailed in the end-of-study analysis SAP prior to the end-of-study database lock.

Categorical analyses of slowing cognitive and functional decline will be conducted comparing proportions of patients reaching certain levels of decline between AZD3293 treatment groups and the placebo group. The precise definitions of cognitive and functional decline and analysis methods will be detailed in the SAP prior to database lock.

The ADAS-Cog₁₃ total score results for change from baseline at Week 104 will be assessed for consistency among subgroups defined by disease status at baseline (MCI due to AD or mild AD), APOE4 status (carrier versus non-carrier), age, race, sex, region, and acetylcholinesterase inhibitor use at baseline (yes or no).

Exploratory analyses of the NPI total score will be conducted; some of these analyses will be limited to the domains that are most prevalent at baseline. Exploratory analyses of the ADCS-ADL basic items score and total score will also be conducted. In an additional exploratory analysis, the proportion of patients with MCI due to AD who progress to mild AD, as assessed by the NIA-AA diagnostic criteria, over 1 year and 2 years, will be examined. The Statistical Analysis Plan will provide further details of these analyses.

Exploratory efficacy variables (see Section 6.3.3) will be analyzed using the MMRM models described above as well as with descriptive statistical analyses. These variables include changes from screening/baseline to Week 104 that include but are not limited to: the Letter Fluency, Category Fluency, and Digit Symbol-Coding test scores, the NPI-D score, as well as the changes over time from screening to Week 97 in the RBANS score.

12.2.5. Biomarkers

Changes from screening to Week 97 in CSF biomarkers (eg, $A\beta_{1-42}$, total tau, and phosphorylated tau) will be analyzed using an MMRM analysis that includes the fixed effects of treatment, visit (categorical covariate), treatment-by-visit interaction, disease status at baseline (MCI due to AD or mild AD), APOE4 status (carrier versus noncarrier), and predose biomarker value (continuous covariate). An unstructured variance-covariance matrix will be used. The primary analysis is based on the treatment difference at Week 97 using least-squares means. The null hypothesis is that the difference in means between the AZD3293 group and placebo equals zero.

The primary analyses of estimates of global cortical load from amyloid PET and volumetric brain measures from MRI will be analyzed using the same methodology as described above for the CSF biomarker data.

In addition, amyloid PET data, including inter-individual patterns of baseline cortical load and intra-individual patterns of regional amyloid deposition, as well as eventual patient-level or regional differences in the longitudinal change of amyloid, will be explored in relation to AZD3293 treatment. Multivariate regression analysis will be performed on the level of global cortical amyloid load, the level of regional measures of amyloid binding and, potentially, on the level of single volume elements (voxels) of amyloid binding (parametric) images. Other imaging (ie, volumetric MRI) and non-imaging (eg, CSF biomarker, cognitive, demographic) data may also be explored as covariates in the analysis model.

12.2.6. Health economics

For the RUD-Lite, the individual item responses and the total study partner time spent in assisting the patient, as well as changes from baseline in these variables, will be summarized by treatment group and time point using descriptive statistics.

For the EQ-5D-5L and EQ VAS responses and changes from baseline will be summarized by treatment group and time point using descriptive statistics.

12.2.7. Pharmacokinetics

Plasma and CSF AZD3293 and AZ13569724 concentrations will be summarized by treatment and time point using descriptive statistics.

The results of the population PK analyses described in Section 11.3 will be summarized in a separate report.

12.2.8. Pharmacokinetics-pharmacodynamics

It is intended that an early lock of the PK data will be conducted to allow PK modeling to begin before the end of the treatment period and to ensure that exposure estimates from this study are available for use in exposure-response models examining the influence of PK on either efficacy or safety endpoints at the completion of the study. It is intended that the PK data will be locked after all patients complete Visit 16 (78 weeks of treatment). No safety or efficacy data will be included in the 78-week PK lock. An Early PK Lock Plan will be developed and implemented prior to this lock, which will specify the safeguards to be taken to ensure the integrity of the study. The results of the population PK/PD analysis described in Section 11.4.4 will be summarized in a separate report.

12.2.9. Pharmacogenomics

The analysis of pharmacogenomics (DNA) outcomes will consist of an analysis of the association of baseline variation with chosen outcome parameters, including efficacy and biomarker outcomes. The analysis of mRNA and miRNA outcomes will consist of descriptive statistics regarding change from baseline, including stratification by endpoints. Pharmacogenomics outcomes will be tested in a prioritized list of genes for which a scientific hypothesis for interaction with the pharmacology of AZD3293 and/or the pathophysiology of AD can be formulated, based on knowledge in the field. The results will be summarized in a separate report. Both univariate statistics and multivariate models may be applied.

12.2.10. Safety

The incidence and severity of treatment-emergent AEs will be summarized by treatment group. The results of clinical laboratory tests; 12-lead ECGs; physical, eye, skin, and neurological examinations; safety MRIs; suicidality evaluations (C-SSRS), body weight and body mass index; and vital sign measurements will be summarized with descriptive statistics, by treatment group, for all time points at which these variables are collected. In addition, visual displays of the time course of AEs will be generated, and analyses that account for time on study will be conducted.

Individual patient data for vital signs, ECG results, and laboratory test results will be assessed for PCS values according to predetermined criteria. Any PCS values identified will be summarized by treatment group.

12.3. Determination of sample size

12.3.1. Efficacy

The sample size for this study, 734 randomized patients in each of 3 treatment groups, was selected to be consistent with the hypothesis described in Section 1.2. The sample-size calculations are based on the primary efficacy endpoint, change from baseline in ADAS-Cog₁₃ total score at Week 104.

Assumptions about minimally clinically significant differences as measured by the ADAS-Cog total score were based on 18 month solanezumab results extrapolated to 24 months. In this database, the least-squares treatment difference from placebo in mean change in ADAS-Cog total score from baseline at 80 weeks in the mild AD population of APOE4 carriers with CDR global score = 0.5 was 1.68 units with a standard deviation (SD) of 9.72. A linear extrapolation using these results coupled with results at 28 and 52 weeks resulted in 104 week estimates of 2.24 (12.96). Using these estimates to approximate an MCI population, this expected difference translates into an effect size of 0.17.

Compared with the MCI population, deterioration of cognition in patients with mild AD has been observed to be somewhat faster. The least-squares treatment difference from placebo in mean change in ADAS-Cog total score from baseline at 80 weeks in the solanezumab mild AD population (enriched by restricting to APOE4 carriers) was 2.87 (10.16) units. A linear extrapolation using these results coupled with results at 28 and 52 weeks resulted in 104 week estimates of 3.83 (13.54). This expected difference translates into an effect size of 0.28.

Similar calculations were made for the key secondary endpoint ADCS-iADL. The least-squares mean change in ADCS-iADL score from baseline at 80 weeks in the mild placebo-treated population of APOE4 carriers with CDR global score = 0.5 was 0.31 (8.39) units. A linear extrapolation using these results coupled with results at 28 and 52 weeks resulted in 104 week estimates of 0.41 (11.19). Using these estimates to approximate an MCI population, this expected difference translates into an effect size of 0.04. The least-squares mean change in ADCS iADL score from baseline at 80 weeks in the mild AD population (enriched by restricting to APOE4 carriers) was 2.14 (9.81) units. A linear extrapolation using these results coupled with results at 28 and 52 weeks resulted in 104 week estimates of 2.85 (13.08). This expected difference translates into an effect size of 0.22.

The study will enroll a total of 2202 patients (734 patients per group). Assuming α =0.025 and the effect size among the patients who discontinue without completing the study is 50% of the effect size of the completers, the power for the mixture of MCI and mild AD patients for a single dose is 96% for ADAS-Cog (adjusted effect size is 0.21); for iADL it is 60% (adjusted effect size is 0.13). The power to show statistical significance for the mild AD subpopulation is 93% (adjusted effect size is 0.24) and 75% (adjusted effect size is 0.19) for ADAS-Cog and iADL, respectively. The power to show statistical significance for the MCI subpopulation is 26% (adjusted effect size is 0.14) and 3% (adjusted effect size is 0.03) for ADAS-Cog and iADL, respectively (Table 7).

Population	ADAS-Cog ES per Dose	ADAS-Cog Power per Dose	ADCS-iADL ES per Dose	ADCS-iADL Power per Dose
Overall*	0.21	96%	0.13	60%
Mild AD	0.24	93%	0.19	75%
MCI	0.14	26%	0.03	3%

Table 7. Effect Size and Power per Dose for Mild AD and MCI Patient Populations

Abbreviations: AD Alzheimer's Disease; ADAS-Cog Alzheimer's Disease Assessment Scale-Cognition; ADCS-iADL The Alzheimer's Disease Cooperative Study Activities of Daily Living Inventory - instrumental items score; ES Effect size; MCI Mild cognitive impairment.

12.3.2. Biomarkers

This section summarizes the sample-size estimates and power calculations for biomarkers arising from the CSF and PET sub-studies and for volumetric MRI data. All biomarker analyses will use α =0.05 (2-sided).

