This study will be randomized, double blind, and placebo controlled. Randomization and blinding of the patient, the patient's study partner, the investigator, and the Sponsor to the patient's treatment assignment are intended to minimize the potential for bias in the analysis of AZD3293 treatment effects. The placebo comparator will provide a reference for the changes in cognition and biomarkers due to disease progression as well as inform the safety profile of AZD3293 in patients with early AD.

Dosing and study duration

The AZD3293 doses selected for this study (20 mg and 50 mg, administered once daily) represent the projected therapeutic dose range based on their levels of inhibition of BACE1 in the CNS as calculated from the multiple-ascending-dose study CSF A β data. It is anticipated that 20-mg and 50-mg AZD3293 doses should achieve clinically relevant CSF A β reductions,

and the projected mean exposures at those doses should be well within the range of exposures shown to be safe and well tolerated in the Phase 1 studies. The 20-mg dose provided >50% mean reduction in CSF A β 1-42 concentrations over the dosing interval, and the 50-mg dose provided approximately 75% reduction in CSF A β 1-42 concentrations over the dosing interval. Thus, these 2 doses are deemed sufficient to demonstrate the efficacy of AZD3293 in this study. The PK variability is expected to be sufficiently low to ensure that individual patient exposures at these doses will also not exceed the levels already demonstrated to be safe and well tolerated.

The 104-week study duration is deemed adequate to detect the effects of AZD3293 on cognition, function, and biomarkers relevant to AD in the selected patient population. The potential for debilitating disease progression in the placebo-treated patients will be mitigated by the fact that all study patients will be maintained on standard of care.

Primary endpoint

The primary endpoint in this study is the change from baseline to Week 104 in the ADAS-Cog₁₃. The ADAS-Cog is a widely accepted, validated clinical outcome measure. The scale reflects domains and abilities that are central to the characterization of an AD patient's deficits in a clinical setting and its items are linked to meaningful aspects of the lives of patients and caregivers. Furthermore, the scale has demonstrated its ability to detect treatment differences in the span of MCI and mild AD (Orgogozo et al. 2004; Salloway et al. 2004; Aronson et al. 2009).

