12.2.3. Multiplicity adjustments

The proposed study design contains several elements that require multiplicity adjustments to strongly control the family-wise error rate (FWER):

- Comparison of 2 AZD3293 treatment groups with the placebo group
- Changing the randomization ratio to 2:1 if a dose is dropped at the first or second interim analysis
- Sample size re-estimation at the second interim analysis

The first element, comparisons of the 2 AZD3293 treatment groups with the placebo group, is addressed by the use of a multiplicity graph. A graphical multiplicity strategy will be used for testing key secondary hypotheses to protect against Type I error of falsely rejecting a null hypothesis. The use of a prespecified analysis plan that employs Bretz' graphical approach will provide strong control of the study-wise Type I error rate for the primary and key secondary hypotheses at level α =0.05 (Bretz et al. 2009, 2011). The specific multiplicity graph will be detailed in the SAP.

In addition, to strongly control the FWER, a confirmatory adaptive design should satisfy the conditional invariance principle (Brannath et al 2007): separate test statistics will be calculated from the 2 patient cohorts (those patients enrolled prior to the second interim analysis [IA2], and those enrolled after IA2) and combined in a prespecified way (using the weighted inverse normal p-value combination method) for the final test decisions. Hence, any design modification that preserves the distributional properties of the separate test statistics under a given null hypothesis of interest will not lead to an inflation of the FWER. The p-value combination test principle combines the 2 p-values using a prespecified combination function and by construction satisfies the invariance principle. Details on the implementation of the measures to strongly control the FWER will be provided in the statistical analysis plan

A separate family of biomarkers will be tested at α =0.05. The family will include the biochemical biomarkers (CSF A β 1-42, total tau, and phosphorylated tau), as well as imaging biomarkers (amyloid PET and volumetric MRI).

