12.3.2.1. CSF biomarkers

It is expected that at least 175 patients will be included in the CSF sub-study. Three CSF biomarkers will be assessed: $A\beta_{1-42}$, total tau, and phosphorylated tau. Assuming a 40% missed post-baseline test rate, approximately 35 patients per treatment group will have a baseline value and a post-randomization value. Estimated treatment differences are based on data from the Alzheimer's Disease Neuroimaging Initiative Pool C (www.adni-info.org).

The expected mean (SD) change in CSF $A\beta_{1-42}$ over 104 weeks is -164 (63.25) units. The minimum detectable AZD3293 difference from placebo is 49.72 units (30% reduction) with 90% power and 43 units (26% reduction) with 80% power, α =0.05 (2-sided, t-test).

The expected mean (SD) change in CSF total tau over 104 weeks is -103 (61) units. The minimum detectable AZD3293 difference from placebo is 41.4 units (47% reduction) with 90% power and 43 units (40% reduction) with 80% power, α=0.05 (2-sided, t-test).

The expected mean (SD) change in CSF phosphorylated tau over 104 weeks is -36 (18) units. The minimum detectable AZD3293 difference from placebo is 14 units (39% reduction) with 90% power and 12 units (33% reduction) with 80% power, α =0.05 (2-sided, t-test).

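### CSF total tau power is misprinted: 41.4 units has 80% power, not 90%, and the larger 43 units cannot have less power than the smaller difference

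*Protocol*

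**What the plan says.** Section 12.3.2 of the Protocol fixes the significance level for the biomarker calculations: "All biomarker analyses will use α =0.05 (2-sided". Section 12.3.2.1 then deals with three CSF markers. It expects at least 175 patients in the sub-study and a 40% rate of missed post-baseline tests, leaving about 35 evaluable patients per treatment group. For each marker it states an expected mean change with its SD, then the smallest difference from placebo detectable with 90% and with 80% power, in units and as a percentage.

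- **Aβ1-42**, mean change 164 in size, SD 63.25: "The minimum detectable AZD3293 difference from placebo is 49.72 units (30% reduction) with 90% power and 43 units (26% reduction) with 80% power".
- **Total tau**, mean change 103 in size, SD 61: "41.4 units (47% reduction) with 90% power and 43 units (40% reduction) with 80% power".
- **Phosphorylated tau**, mean change 36 in size, SD 18: "The minimum detectable AZD3293 difference from placebo is 14 units (39% reduction) with 90% power and 12 units (33% reduction) with 80% power".

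**The concern.** For Aβ1-42 and phosphorylated tau, the larger difference goes with the higher power, as it must. For total tau the order is reversed. The text also contradicts itself on the percentages, since 41.4 is printed as a larger percentage reduction (47%) than 43 (40%).

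The consequence is limited but runs in the optimistic direction. Total tau is one of the five markers in the separate biomarker family of Section 12.2.3. A reader who takes the 90% figure at face value will think the CSF sub-study more sensitive to a total tau effect than it is, and may read too much into a null result.

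**Working it through.** **Inputs (Section 12.3.2.1).** Evaluable patients per group: 175 × 0.6 / 3 = 35. Test: two-sided t-test at 0.05, one AZD3293 group against placebo, so df = 2 × 35 − 2 = 68 and the critical value is about 1.995. Means and SDs are as listed above.

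**Formula.** The noncentrality is δ = d / (SD × √(2/35)), where √(2/35) = 0.2390. Power is the probability that a noncentral t with 68 df and noncentrality δ exceeds the critical value.

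**Step 1: reproduce the neighbouring lines.**

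| Marker | Difference | Share of mean | Printed power | Recomputed |
|---|---|---|---|---|
| Aβ1-42 | 49.72 | 49.72/164 = 30% | 90% | 90.0% |
| Aβ1-42 | 43 | 43/164 = 26% | 80% | 80.1% |
| Phosphorylated tau | 14 | 14/36 = 39% | 90% | 89.4% |
| Phosphorylated tau | 12 | 12/36 = 33% | 80% | 78.5% |

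The method is therefore the protocol's own, and each percentage is the difference divided by the expected mean change. The small gaps for phosphorylated tau are rounding: the exact differences are 14.15 and 12.23 units.

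**Step 2: total tau as printed.** The standard error is 61 × 0.2390 = 14.58.

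| Difference | δ | Share of 103 | Printed share | Printed power | Recomputed |
|---|---|---|---|---|---|
| 41.4 | 41.4/14.58 = 2.84 | 40.2% | 47% | 90% | 79.9% |
| 43 | 43/14.58 = 2.95 | 41.7% | 40% | 80% | 82.8% |

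Neither line agrees with its printed power or its printed percentage. No other single mean rescues the percentages, because 41.4/0.47 = 88 and 43/0.40 = 107.5.

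**Step 3: solve for the differences.** With SD 61, 90% power needs 47.9 units (47.9/103 = 46.6%, which rounds to 47%). Power of 80% needs 41.4 units (41.4/103 = 40.2%, which rounds to 40%). Both printed percentages fall into place.

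**Step 4: a check without power software.** Group size, alpha and test are shared, so the detectable difference is proportional to the SD. The Aβ1-42 line gives 49.72/63.25 = 0.786 SD for 90% power and 43/63.25 = 0.680 SD for 80%. Applied to SD 61, these give 47.9 and 41.5 units, matching Step 3 within rounding.

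**Step 5: where the numbers may have come from.** The value 41.4 is the correct 80% entry, standing in the 90% position. The value 43 equals the Aβ1-42 80% entry in the paragraph above (42.97 unrounded), so it may have been carried over. That is inference, and the error does not depend on it.

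**The case against.** **It is only a slip.** The percentages are right, no sample size is derived from this line, and total tau is not the primary endpoint. All of that stands and limits the importance of the point, but the printed power statement is still wrong.

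**Another basis might explain the pair.** Pooling the two doses (35 against 70) gives 90.1% at 41.4 units, which looks like a match, but it gives 92.1% at 43 units, not 80%. One-sided 0.05 gives 87.8% and 89.9%. Group sizes of 30, 40 and 58 give 73%/77%, 85%/88% and 95%/96%. No common basis can work, because power rises with the difference.

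**A reader might infer something broader:** that all the biomarker powers are overstated. Section 12.3.1 works at the stricter level ("Assuming α =0.025 and the effect size among the patients who discontinue"), whereas Section 12.3.2 uses 0.05 for each comparison although there are two doses and five markers. The documents do not support calling this an error. Each biomarker line prints its own two-sided 0.05, so the basis is visible. Section 12.2.3 treats these markers apart from the efficacy hypotheses ("A separate family of biomarkers will be tested at" 0.05), and nothing there splits that family by dose at 0.025. An ordered procedure within the family would let both statements of 0.05 stand, and Section 12.2.3 leaves the details of error control to the SAP.

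**The MRI figure is not a second case.** In Section 12.3.2.3 the recomputed power is 98.7% against a printed value above 99%. That gap is too small to matter when the group size is itself approximate.

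**Conclusion.** The total tau pair in Section 12.3.2.1 is wrong as printed. The reversed order shows this without calculation, and the recalculation shows which parts are misplaced. At 41.4 units the power is 80%, so the risk of missing a true difference of that size is 20% rather than 10%. Reaching 90% power takes 47.9 units, which is 6.5 units or 16% more than printed (6.5/41.4).

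These figures rest on the protocol's own assumptions: 35 evaluable patients in each of two groups, a common SD of 61, and a two-sided t-test at 0.05. The conclusion covers total tau only and does not extend to the alpha used for the biomarkers or to the power of the other markers.

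**What to change.** In the total tau paragraph of Section 12.3.2.1, restate the minimum detectable difference as 48 units (47% of the expected change) for 90% power and 41.4 units (40%) for 80% power. The rounded 48 units gives 90.1% power. The mean, SD, alpha and test stay as written, and no other biomarker line needs to change.

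The cost is one corrected pair of numbers, with no change to sample size, sub-study enrollment, conduct or analysis.

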12.3.2.1. CSF biomarkers

It is expected that at least 175 patients will be included in the CSF sub-study. Three CSF biomarkers will be assessed: $A\beta_{1-42}$, total tau, and phosphorylated tau. Assuming a 40% missed post-baseline test rate, approximately 35 patients per treatment group will have a baseline value and a post-randomization value. Estimated treatment differences are based on data from the Alzheimer's Disease Neuroimaging Initiative Pool C (www.adni-info.org).

The expected mean (SD) change in CSF $A\beta_{1-42}$ over 104 weeks is -164 (63.25) units. The minimum detectable AZD3293 difference from placebo is 49.72 units (30% reduction) with 90% power and 43 units (26% reduction) with 80% power, α =0.05 (2-sided, t-test).

The expected mean (SD) change in CSF total tau over 104 weeks is -103 (61) units. The minimum detectable AZD3293 difference from placebo is 41.4 units (47% reduction) with 90% power and 43 units (40% reduction) with 80% power, α=0.05 (2-sided, t-test).

The expected mean (SD) change in CSF phosphorylated tau over 104 weeks is -36 (18) units. The minimum detectable AZD3293 difference from placebo is 14 units (39% reduction) with 90% power and 12 units (33% reduction) with 80% power, α =0.05 (2-sided, t-test).

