6.6.1. Cerebrospinal fluid biomarkers

Participants in the CSF longitudinal biomarker sub-study will have post-baseline CSF samples collected at Week 52 and Week 97 (or at discontinuation of study treatment if it has been at least 24 weeks since previous collection) for analysis of concentrations of $A\beta_{1-40}$, $A\beta_{1-42}$, total tau, phosphorylated tau, and exploratory biomarkers (eg, sAPP β , sAPP α , 5-x amyloid) (see Study Plan in Table 2). If a post-baseline CSF sample cannot be obtained because of procedural complications, patient issues, or patient request, it will not be considered a protocol violation.

Lumbar punctures should be scheduled at approximately the same time of the day at all visits to avoid the known circadian variation of CSF amyloid levels (Lucey and Bateman 2014). It is recommended that CSF samples be collected by insertion of an atraumatic spinal needle between vertebrae L3 and L5 (Vanderstichele et al 2012). Before performing the lumbar puncture procedure, the physician must take into account the overall assessment of the patient and bleeding risk.

CSF $A\beta_{1-40}$ and $A\beta_{1-42}$ are biomarkers for BACE inhibition that enable direct measure of the central PD of AZD3293.

CSF tau and phosphorylated tau concentrations are elevated in patients with AD. Elevations in concentrations of tau, as well as specific phosphorylated tau species, are thought to be markers for progressive neurodegeneration in AD. Accordingly, reductions from baseline in concentrations of CSF tau in patients who receive AZD3293 compared with patients who receive placebo may be indicative of reduced neuronal loss in AZD3293-treated patients.

Other CSF metabolites and/or protein species, including processed forms of APP such as sAPP β , inflammatory biomarkers, other recognized or as-yet unrecognized biomarkers, and, if appropriate, proteomics assessments may be examined. Biochemical signatures may help to explain differences in efficacy, safety, or tolerability and/or PK/PD related to AZD3293 treatment.

Detailed sample collection and handling procedures are provided in the Laboratory Manual.

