11.4. Calculation or derivation of pharmacodynamic variable(s)

11.4.1. Cerebrospinal fluid biomarkers

Changes from screening in CSF biomarker concentrations of $A\beta_{1-40}$, $A\beta_{1-42}$, total tau, phosphorylated tau and other, exploratory biomarkers (eg, sAPP β) will be calculated for each post-baseline time point.

Changes in biomarker concentration will be calculated as the post-baseline value minus the predose value.

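### CSF total tau: the stated detectable differences do not follow from the protocol's own inputs, and the CSF reference changes are given without arm or direction

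*Protocol*

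**What the plan says.** Protocol Section 12.3.2.1 sets out the power of the CSF sub-study of at least 175 patients. On numbers: "Assuming a 40% missed post-baseline test rate, approximately 35 patients per treatment group will have a baseline value and a post-randomization value". The test is a two-sided t-test at alpha 0.05.

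For each marker the section gives an expected mean change with its SD, then a detectable difference from placebo with a percent reduction in brackets:

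- Aβ1-42, with an expected change of -164 (SD 63.25), has these detectable differences: "The minimum detectable AZD3293 difference from placebo is 49.72 units (30% reduction) with 90% power and 43 units (26% reduction) with 80% power".
- Total tau has these detectable differences: "The minimum detectable AZD3293 difference from placebo is 41.4 units (47% reduction) with 90% power and 43 units (40% reduction) with 80% power". The reference behind them is given as follows: "The expected mean (SD) change in CSF total tau over 104 weeks is -103 (61) units".
- Phosphorylated tau has these detectable differences: "The minimum detectable AZD3293 difference from placebo is 14 units (39% reduction) with 90% power and 12 units (33% reduction) with 80% power". Its reference is given in the same form: "The expected mean (SD) change in CSF phosphorylated tau over 104 weeks is -36 (18) units".

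No arm is named for any of the three means. Two other sections bear on how to read them. Section 11.4.1 fixes the sign: "Changes in biomarker concentration will be calculated as the post-baseline value minus the predose value". Section 6.6.1 takes raised tau as a marker of progressive neurodegeneration and describes the hoped-for effect as "reductions from baseline in concentrations of CSF tau in patients who receive AZD3293 compared with patients who receive placebo".

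**The concern.** There are two separate problems in one paragraph.

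The first is arithmetic. For a fixed SD, sample size and alpha, the detectable difference must grow as the required power grows. For total tau it shrinks, from 43 units at 80% power to 41.4 at 90%. The unit figures also disagree with the percentages beside them.

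The second is interpretation. Under Section 11.4.1 a negative change is a fall, and the percentages are shares of that fall. Sections 12.3.2.2 (PET) and 12.3.2.3 (MRI) have the same layout, but there the reference is labelled as a placebo change and a reduction means a smaller change on drug. Carried over to tau, a 47% reduction of a 103-unit fall means tau falls less on drug than on placebo, which is the opposite of the benefit in Section 6.6.1.

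All three markers belong to the biomarker family tested at alpha 0.05 (Section 12.2.3), and this paragraph is the power rationale for the sub-study. As it stands, a reader cannot tell which arm the reference belongs to or which direction of effect is being powered, and is given the wrong detectable difference for total tau.

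**Working it through.** **Inputs** (Section 12.3.2.1 unless noted)

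- Evaluable per arm: 175 × 0.60 / 3 = 35 (1:1:1 allocation, Section 3.1).
- SD of change: 63.25, 61 and 18.
- Two-sided alpha 0.05 (Section 12.3.2). Two-sample t-test, 68 degrees of freedom, critical value 1.995.

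**Formula.** Power is the probability that a noncentral t variable with 68 df and noncentrality δ / (SD × √(2/35)) exceeds 1.995. Solving for δ gives 0.786 × SD at 90% power and 0.679 × SD at 80%. The mean change does not appear.

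**Reproducing the protocol's figures**

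| Marker | Power claimed | Stated units (%) | Recomputed units | Recomputed ÷ size of mean | Actual power of stated units |
|---|---|---|---|---|---|
| Aβ1-42 | 90% | 49.72 (30%) | 49.72 | 30% | 90.0% |
| Aβ1-42 | 80% | 43 (26%) | 42.97 | 26% | 80.1% |
| Total tau | 90% | 41.4 (47%) | 47.95 | 47% | **79.9%** |
| Total tau | 80% | 43 (40%) | 41.44 | 40% | **82.8%** |
| Phosphorylated tau | 90% | 14 (39%) | 14.15 | 39% | 89.4% |
| Phosphorylated tau | 80% | 12 (33%) | 12.23 | 34% | 78.5% |

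Aβ1-42 reproduces exactly and phosphorylated tau reproduces within rounding, so the method is the protocol's own. Total tau does not reproduce. Its stated units also fail against its stated percentages: 41.4/103 = 40%, not 47%, and 43/103 = 42%, not 40%. The percentages match the recomputed units: 47.95/103 = 47% and 41.44/103 = 40%. So the percentages are right and the units are wrong. The 41.4 is the 80%-power value placed against 90%, and the 43 coincides with the Aβ1-42 value at 80%.

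Other settings do not rescue the figures. One-sided alpha 0.05 gives 87.8% power for 41.4 and 89.9% for 43. No change of n, alpha or SD can make a smaller difference the one detectable at higher power.

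**What the percentages mean.** The table shows that each percentage is the detectable difference divided by the size of the expected change. The PET and MRI sections work the same way with a labelled placebo change: 0.041/0.0484 = 85% and 1.367/7.565 = 18%.

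Take total tau with the 80%-power difference of 41.4:

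- Reference -103 on placebo, change made smaller: -103 + 41.4 = -61.6. Tau falls less on drug.
- Reference -103 on placebo, further fall: -103 - 41.4 = -144.4. Tau falls more on drug.
- Reference +103 on placebo, change made smaller: 103 - 41.4 = +61.6. Tau rises less on drug.

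Only the second and third agree with Section 6.6.1. The first is what the PET and MRI layout implies when applied to the printed sign.

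**Effect of the sign.** Reversing it leaves every detectable difference, every power and the size of every percentage unchanged, because the two-sided test uses only SD, n and alpha.

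**The case against.** The strongest reply on the interpretive part is that the protocol never says these are untreated changes. The PET and MRI sections name placebo; the CSF section does not. The test is two-sided, and the word reduction can be read as a further lowering relative to placebo, which agrees with Section 6.6.1. Nor does any section state how CSF tau moves over two years without treatment, so nothing in the protocol refutes -103. All of this stands, and it limits the point to an ambiguity that needs resolving.

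Three stronger inferences are tempting and should not be drawn:

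- *The sub-study is powered for a harmful effect.* This depends on one reading of an unlabelled mean.
- *The SDs are unreliable because the means look odd.* The protocol labels them as SDs of change, and they reproduce the Aβ1-42 and phosphorylated tau figures. That shows they were used in the calculation. It does not verify their source, but nothing in the protocol shows that they are wrong.
- *The Aβ1-42 figure of 30% contradicts Section 3.3*, which cites reductions of more than 50% and about 75%. Those are reductions in concentration over the dosing interval, whereas 30% is a share of a change score. The denominators differ.

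It can also be said that a biomarker power paragraph affects no patient number. That is correct, and it bears on severity. It does not answer the total tau error, which needs no reading of arm or sign.

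**Conclusion.** The total tau figures are wrong on the protocol's own inputs. The difference stated for 90% power is too small by 47.95 - 41.4 = 6.55 units and has about 80% power. The difference stated for 80% power is too large by 43 - 41.44 = 1.56 units and has about 83% power. This rests only on SD 61, 35 per arm and two-sided alpha 0.05, all from the protocol.

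The three reference means are inadequately specified. Under Section 11.4.1 they are falls. If they are placebo changes and a reduction means a smaller change, the tau percentages run against Section 6.6.1. Whether they are placebo changes, on-drug changes or concentrations cannot be settled from the document. This is a defect of labelling and direction. It changes no detectable difference, power or patient number unless the SDs turn out not to be SDs of within-patient change.

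**What to change.** In Section 12.3.2.1:

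1. Restate total tau as about 47.9 units (47%) at 90% power and 41.4 units (40%) at 80% power.
2. For each marker, state which arm the reference mean describes and give its sign under the Section 11.4.1 definition.
3. Confirm from the source data that each SD is the SD of within-patient change. If one is not, replace it and recompute that marker's two differences as 0.786 × SD and 0.679 × SD.
4. Express each detectable effect as a signed difference from placebo. For tau, use the direction that Section 6.6.1 treats as benefit. For Aβ1-42, state the intended direction explicitly.
5. If a reference mean is not a placebo change, drop its percentages, including those restated in item 1.

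The cost is a short recalculation and a wording change. No change to enrolment is needed.
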